7.4. QT-RELATED POLYMORPHISMS ASSESSMENT

A 10 mL blood sample will be collected on Day 1 from patients who consented to take part in the QT-related polymorphisms assessment of the substudy at the time point indicated in the substudy's Schedule of Assessments and Procedures (see below). Participation in the QT-related polymorphisms assessment is optional.

A manual of instructions for sample collection, labeling, storage, and shipment will be provided as a separate document (Instruction Manual for the Collection, Labeling, Storage and Shipment of Pharmacokinetic Samples).

If a patient shows marked drug-related changes of the QTc interval and a genetic cause is suspected, that individual sample will be analyzed.

Genes currently hypothesized to potentially be relevant to irregular QT/QTc intervals such as KCNE1, KCNE2, KCNH2, KCNQ1 and SCN5A will be considered for genotyping.

When the ECG database will be locked, if no marked drug-related changes are observed, all samples for QT-related polymorphisms assessment from the substudy will be destroyed.

7.4.1. Confidentiality of Samples for QT-related Polymorphisms Assessment

PharmaMar shall comply with the Directive 95/46/EC of the European Parliament and of the Council of 24 October 1995 on the protection of individuals with regard to the processing of personal data and on the free movement of such data.

Appropriate technical and organizational measures to protect the genetic data against unauthorized disclosures or access, accidental or unlawful destruction, or accidental loss or alteration will be put in place. Sponsor personnel whose responsibilities require access to personal data agree to keep the identity of substudy patients confidential.

Samples will be stored until the ECG database has been locked, when the decision on whether it is necessary to rule out mutations associated with ion channelopathies, is made.

7.5. 12-LEAD ECG ACQUISITION

ECGs will be obtained digitally using a Mortara Instrument (Milwaukee, WI, USA) H-12+ ECG continuous 12 lead digital recorder, which will obtain ECGs on Day 1 and Day 15. The ECGs are stored continuously on a flash card and will not be available for review until the card is received by ERT and analyzed. ECGs to be used in the analysis will be selected by predetermined time points as detailed below and will be read centrally using a high-resolution manual on-screen caliper semiautomatic method with annotations. In this trial using pre-treatment ECGs as the baseline, the H-12+ recording will be started approximately 1 hour prior SOI through approximately 21 hours post EOI in order to obtain the baseline ECGs as detailed below.

ECGs for the treatment days will be obtained as triplicate (3) 12-lead ECGs at each time point which will be downloaded from the H-12+ flash card approximately one minute apart on Day 1 and Day 15. On Day 1 and Day 15, baseline ECGs will be extracted (in triplicate) pre-prophylaxis (Predose 1), post-prophylaxis and prior to SOI (Predose 2). On Day 1 and Day 15, triplicate ECGs will be extracted at the following time points: 1.5 after SOI, just before the EOI, 0.5, 1, 3, 6, 9 and 21 hours after EOI.

7.6. ECG ANALYSIS METHODS

ECGs will be sent to ERT for a treatment-blinded high-resolution measurement of the cardiac intervals, and morphological assessment by a central cardiologist.

The 12-lead digital continuous ECG signal for each session in each patient will be recorded on compact flash memory cards provided to the site. The patient's unique identification number and demographic information will be recorded for each card. ERT will generate a 10-second, 12-lead digital ECG at each time point specified in the protocol. If targeted ECG time points are artifactual and of poor quality, ERT will capture analyzable 10-second ECGs as close as possible to the targeted time points.

Digital ECGs will be transmitted to ERT's validated data management system, EXPERT. Interval duration measurements will be collected using computer assisted caliper placements on three consecutive beats. Trained analysts will then review all ECGs for correct lead and beat placement and will adjudicate the pre-placed algorithm calipers as necessary using the proprietary validated electronic caliper system applied on a computer screen. A cardiologist will then verify the interval durations and perform the morphology analysis, noting any T-U wave complex that is compatible with an effect on cardiac repolarization.

The ECG analysis will be conducted in Lead II, or in Lead V5 if Lead II is not analyzable. If Lead V5 is not analyzable then Lead V2 will be used, followed by the most appropriate lead if necessary. ECG readers will be blinded to patient identifiers, and visit. All ECGs for a given patient will be analyzed by the same reader. Quality Assurance reports for inter- and intra-observer variability will be produced by the central ECG laboratory and provided to the Sponsor.

On-screen measurements of the RR, PR, QRS, and QT interval durations will be performed and variables for QTcF, QTcB, and heart rate (HR) will be obtained by the following processes:

Interval measurements will be obtained by the following method:

•	Three (3) RR	mean RR Interval is reported.
---	--------------	-------------------------------

- Three (3) PR mean PR Interval is reported.
- Three (3) QRS mean QRS Width is reported.
- Three (3) QT mean QT Interval is reported.

The following calculations will be made from the interval measurements:

Three (3) QTcF measurements- QTc correction by the Fridericia's formula

- QTcF1 = QT1/ $^{3}\sqrt{RR1}$
- $QTcF2 = QT2/^3 \sqrt{RR2}$
- $QTcF3 = QT3/^3 \sqrt{RR3}$
- Mean QTcF = (QTcF1 + QTcF2 + QTcF3)/3

Three (3) QTcB measurements- QTc correction by the Bazett's formula

- QTcB1 = QT1/ $\sqrt{RR1}$
- $QTcB2 = QT2/\sqrt{RR2}$
- QTcB3 = QT3/ $\sqrt{RR3}$
- Mean QTcB = (QTcB1 + QTcB2 + QTcB3)/3

Three (3) Heart Rate measurements

- HR1 = 60 / RR1
- HR2 = 60 / RR2
- HR3 = 60 / RR3
- Mean HR = (HR1 + HR2 + HR3)/3

Each fiducial point (onset of P wave, onset of Q wave, offset of S wave, and offset of T wave) will be electronically marked. The original ECG waveform and such annotations will be saved separately in XML format for independent review.

8. STATISTICAL METHODS

A non-inferiority limit of 20 ms will be used for the comparison of the effects of plitidepsin on the QT/QTc intervals.

8.1. SAMPLE SIZE

Using a standard deviation of 18 ms in a sample size of 36 evaluable patients, the probability that the upper limit of the one-sided 95% confidence interval (CI) for the difference in mean QTc between each time point and baseline (Δ QTc) will fall below 20 ms is 80%, when the true difference in means equals 5 ms.

8.2. PHARMACODYNAMIC ANALYSES

The primary objective of this substudy is to measure the potential effect of plitidepsin on QTc. The primary comparison of interest will be Δ QTc at each scheduled time point. A non-inferiority criterion of 20 ms will be used to establish that postdose QTc is not inferior to baseline. Evaluable patients who have evaluable ECG data will be included in the primary analysis.

A mixed effect analysis of variance (ANOVA) model will be fitted with the QTc data as the dependent variable and intervention (baseline *vs.* postdose), scheduled time point t of measurement (where t will be baseline, 1.5 after SOI, just before the EOI, 0.5, 1, 3, 6, 9 and 21 hours after EOI) and treatment period (Day 1 and Day 15) as fixed effects and patient as a random effect. Using the estimated least square means and intrapatient variance obtained from this model, a one-sided 95% CI will be calculated for the

difference in mean QTc between baseline and each scheduled time point t. Non-inferiority will be concluded if at each scheduled time point the upper-limit of the one-sided 95% CI falls below 20 ms.

Mean ECG parameters (QT, QTc, RR, heart rate, QRS, and PR) and corresponding changes from baseline will be listed and summarized descriptively by time point t. Plots of mean QTc changes from baseline (Δ QTc) *vs*. the scheduled time point t will be prepared.

The incidence count and percentage of patients with QTc increase from baseline $(\Delta QTc) > 30-60$ ms and >60 ms will be tabulated for each time point t, age and gender. The incidence count and percentage of patients with any postdose QTc values >450 ms and >480 ms, will be tabulated for each time point t, and gender. Patients with QTc values >500 ms will be listed.

The incidence count of patients with PR >200 ms, QRS >120 ms, heart rate >100 bpm and <50 bpm, and ST segment and T and U wave abnormalities will be reported. The incidence count of patients with abnormalities in the ST segment (e.g. flat, depressed, elevated) and T wave (i.e. present or absent) and U wave (e.g. flattened, inverted, biphasic and notched) will be reported.

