1.3.4.2.9 Conclusions on Safety Results

Plitidepsin alone or in combination with carboplatin, dacarbazine or dexamethasone has a tolerable safety profile with most AEs mild to moderate and usually reversible upon drug reduction or discontinuation. The negligible hematological toxicity makes this compound a good candidate for combination with standard chemotherapy.

Overall, the currently available clinical data provide reassurance that the toxicity of plitidepsin appears to be acceptable in the clinical setting.

1.3.4.3 *Summary of Pharmacokinetic Results*

Pharmacokinetic data have been collected from patients in phase I and II studies following i.v. administration of plitidepsin using the following schedules: 24-hour infusion every week (Day 1 and 15 q4wk), 3-hour infusion every other week (Day 1 and 15 q4wk), 1-hour infusion every week (Day 1, 8, 15 q4wk), 24-hour infusion every other week (Day 1 and 15 q4wk) and 1-hour infusion for five consecutive days every three weeks (Day 1-5 q3wk).

After non-compartmental analysis, plitidepsin was found to be widely distributed, with apparent volumes of distribution in steady state (V_{ss}) of about 500 to 1350 l based on plasma, and from about 100 to 225 l based on whole blood, thus suggesting that blood cells are an important distribution compartment. Concentrations were about 3-fold higher in whole blood than in plasma.

This initial characterization was updated after analyzing data from phase II clinical trials, with samples collected at later time points than in the phase I trials. Furthermore, patients included in phase II trials had samples taken for pharmacokinetic (PK) evaluation during both the first and third treatment cycle, allowing for a more extensive analysis. Population methodology was used, as the phase II studies had sparse sampling.

Thus, the population PK analysis of plitidepsin was performed based on data from 13 clinical studies, including all four adult patients, single-agent phase I studies (APL-A-001-98, APL-A-002-98, APL-A-003-98 and APL-A-004-98) and nine phase II studies

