1.2. SUBSTUDY DESIGN RATIONALE

Plitidepsin is an anticancer agent that should not be administered to healthy subjects. Plitidepsin is administered at maximum tolerated dose, so it cannot be tested safely at supratherapeutic concentrations, even in cancer patients.

The impact of the disease, together with age, comorbidities and comedications present in patients with cancer is such that they are unable to tolerate excessive testing. Therefore, the search for a precise characterization of the effects of the drug on the QTc must be carefully balanced against the feasibility of the study design. Furthermore, the duration of the QTc interval is a less-than-perfect marker of the risk of proarrhythmia.[3]

Patients with refractory malignancies and expected reduced survival could justifiably be excused from the burden of time-matched baseline ECG values and separate administration of a positive control.[4]

Therefore, this substudy will be conducted in patients who may benefit from the anticancer activity of plitidepsin at the recommended dose, such as those enrolled in clinical trial APL-C-001-09. The potential effects of a 5 mg/m^2 plitidepsin dose given as a 3-hour intravenous infusion on the QTc interval duration will be assessed when the patient is treated with plitidepsin for the first time (Day 1 of Cycle 1). In order to detect any delayed drug effect on the QTc interval, these investigations will be repeated at the second infusion of plitidepsin (Day 15 of Cycle 1), when the drug is expected to reach the steady state in spite of plitidepsin's long terminal half-life in blood, approximately 88 hours, although concentrations on Day 15 are negligible.

This substudy will be conducted at some of the sites participating in study APL-C-001-09.

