Although the daily variability in QTc interval of cancer patients has not been well described, it may be even larger because enrolled patients are likely to have advanced age, concomitant medical problems and prior QT-prolonging chemotherapy.[5] For this reason, an intrapatient standard deviation of 18 milliseconds is assumed. To reduce intrapatient variability due to measurement error, it has been recommended that the baseline QTc be rigorously investigated and be expressed as the mean of multiple electrocardiogram assessments.[6] For this purpose, two sets of triplicate ECG tracings recorded before plitidepsin administration will be considered baseline assessments: one set before and one after prophylactic medication administration on Days 1 and Day 15.

Electrocardiogram assessments will be performed by means of continuous 12-lead ECG automated digital collection.

All digital ECG continuous recordings will be sent to a third-party central ECG laboratory for measurement of intervals, diagnostics of abnormalities and review of ECG waveform morphology review. This will prevent the potential introduction of bias during the analysis of ECG recordings.

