7.3.2. Pharmacodynamic Endpoints

In principle, for each patient and each postdose time point on Day 1 and Day 15, baseline QTc intervals will be the mean of the Predose 1 and Predose 2 QTc values for that patient on Day 1.

If the mean Predose 2 QTc value of all evaluable patients is ≥ 10 ms longer than of the mean Predose 1 QTc value, an effect of prophylactic medication on QTc cannot be ruled out; therefore, individual Predose 2 QTc values will be considered as the baseline values.

The change from baseline (ΔQTc) will be calculated using the corresponding baseline QTc values. Specifically:

• ΔQTc at time t: Difference in QTc between scheduled time point t and baseline.

The primary pharmacodynamic (PD) endpoint will be ΔQTc at each scheduled time point. ΔQTc will be summarized where QTc is derived using both the QTcF and QTcB correction methods whereby QTc denotes a general notation of corrected QT using either method.

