8.3. PHARMACOKINETIC/PHARMACODYNAMIC ANALYSES

The PK/PD analyses will be based on data collected from the scheduled time points of ECG measurement and:

- 1. their corresponding whole blood plitidepsin concentration.
- 2. their estimated whole blood plitidepsin concentration at the corresponding ECG time point by means of population PK modeling.

Evaluable patients (i.e., those who have evaluable ECG data) who withdraw before completing both days (i.e., Days 1 and 15) will be included in these analyses. Plots of individual QTc changes from baseline (Δ QTc) vs. the corresponding plitidepsin blood concentrations will be prepared to explore any concentration-effect relationship for plitidepsin.

The concentration–QTc relationship will be assessed using a linear mixed effects analysis of the relationship between Δ QTc data and plitidepsin concentration according to the equation: Δ QTc = α + β *[plitidepsin], where inter-individual variability will be estimated for both intercept (α) and slope (β). The effect of treatment period (i.e. Day 1 or Day 15) on slope and intercept will also be evaluated. If the intercept term is not significant, the model will be re-fit with a zero intercept term. The predicted value of Δ QTc (along with 90% CI) will be estimated at the mean maximum plasma (C_{max}) values of plitidepsin.

Additionally, in a complementary PK/PD analysis, the relationship between QTc and plitidepsin whole blood concentration will be assessed using linear mixed effect modeling to estimate the maximal change (mean and upper 95% confidence limit) in the QTc associated with therapeutic concentrations of plitidepsin.

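### The QT substudy's 20 ms rule has no Day 15 contrast, so a delayed QTc rise can pass it; the concentration–QTc prediction also mixes plasma with whole blood

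*Protocol*

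**What the plan says.** All references are to Protocol Appendix 8 unless stated.

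- **Purpose of Day 15** (Section 1.2): "In order to detect any delayed drug effect on the QTc interval, these investigations will be repeated at the second infusion of plitidepsin".
- **Target.** The QT paragraph of the synopsis and Section 7.3.2 define the QTc change at each postdose time point on Day 1 and on Day 15.
- **Model** (Section 8.2): fixed effects for intervention (baseline or postdose), time point (baseline plus eight postdose levels) "and treatment period (Day 1 and Day 15) as fixed effects and patient as a random effect". No interaction is listed. Intervention is fully determined by time point, so it carries no information about day.
- **Decision rule** (Section 8.2): "Non-inferiority will be concluded if at each scheduled time point the upper-limit of the one-sided 95% CI falls below 20 ms".
- **Baseline.** Section 7.3.2 says that for both days "baseline QTc intervals will be the mean of the Predose 1 and Predose 2 QTc values for that patient on Day 1", with a switch to Predose 2 if prophylaxis appears to lengthen QTc. Section 1.2 instead describes two predose sets that "will be considered baseline assessments: one set before and one after prophylactic medication administration on Days 1 and Day 15", and Section 7.5 states: "On Day 1 and Day 15, baseline ECGs will be extracted (in triplicate) pre-prophylaxis".
- **Concentration–QTc model** (Section 8.3): the concentrations are whole blood, measured or model-estimated, but the predicted change "will be estimated at the mean maximum plasma" Cmax. Protocol Section 6 collects uncentrifuged blood only. Protocol Section 1.3.4.3 reports: "Concentrations were about 3-fold higher in whole blood than in plasma".

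**The concern.** With additive time and day effects, the model has one baseline-to-time-point contrast for the two days together. A rise confined to Day 15, which is the event Day 15 was added to find, either goes into the day term, which no limit governs, or is averaged with Day 1. The substudy could therefore conclude non-inferiority while the Day 15 mean is at or above its own 20 ms limit, much more often than a one-sided 95% bound implies.

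The second issue is one of units. A slope estimated per unit of whole-blood concentration and multiplied by a smaller plasma Cmax understates the slope part of the main predicted QTc effect.

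**Working it through.** **Inputs.** N = 36, SD 18 ms, one-sided 95% (z = 1.645), true difference 5 ms and power 80% (Section 8.1); the SD is intrapatient (Section 1.2); limit 20 ms and eight postdose times (Section 8.2).

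**1. The plan's own 80%.** For a paired difference, SE = 18√(2/36) = 4.24 ms. Power at one time point is Φ(15/4.24 − 1.645) = 97.1%. For eight time points taken as independent it is 0.9707⁸ = 78.8%. Two groups of 18 also reproduce the figure: SE = 18√(2/18) = 6.0 and Φ(15/6 − 1.645) = 80.4%. The first route counts eight contrasts, not sixteen.

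**2. What the additive model estimates.** Let the true change be d1 at all Day 1 times and d15 at all Day 15 times.

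- *One Day 1 baseline row.* The day term equals the mean postdose difference, d15 − d1, so the contrast is d1. For 5/25 ms it is 5 ms.
- *Baseline entered for both days.* The contrast is (d1 + d15)/2. For 5/25 it is 15 ms; for 0/22 it is 11 ms.
- *Own-day predose, with the Day 15 predose raised by p.* The contrast is (d1 + d15)/2 − p/2. For 5/25 and p = 20 to 25 it is 5 to 2.5 ms.
- *Excess x at one Day 15 time only.* The contrast at that time is d1 + x/2 with baseline in both days, or d1 + x/2 − x/16 with one Day 1 row (the day term takes x/8, half of which is removed). For d1 = 5 and x = 20 this is 15 or 13.75 ms; for x = 15 it is 12.5 or 11.6 ms.

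**3. Upper limits.**

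- One Day 1 row, single reading: SE = (18/6)√(1/2 + 1/16 + 1) = 3.75 ms. At 5/25 the average limit is 5 + 1.645 × 3.75 = 11.2 ms.
- Baseline in both days: SE = (18/6)√(1/2 + 1/2) = 3.00 ms. At 5/25 the average limit is 15 + 4.9 = 19.9 ms.

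**4. Probability of concluding non-inferiority.** Each case uses 2,000 simulated trials with patient effects and independent residuals. Ranges cover a baseline from one reading or the mean of two, and all codings where so marked. The last column uses 16 time-by-day contrasts against the Day 1 baseline.

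| True change, Day 1 / Day 15 (ms) | Coding | Estimate (ms) | Plan's rule | 16 contrasts |
|---|---|---|---|---|
| 5 / 20 at all times | all | 5 or 12.5 | 43–99% | 0.1% |
| 5 everywhere, 20 at Day 15 end of infusion | all | 11.6–12.5 | 72–84% | 3–5% |
| 5 / 25 at all times | one Day 1 row | 5 | 96–98% | ≤0.3% |
| 5 / 25 at all times | both days | 15 | 7–19% | ≤0.3% |
| 0 / 22 at all times | both days | 11 | 60–70% | ≤0.3% |
| 5 everywhere, 25 at Day 15 end of infusion | all | 14–15 | 49–55% | ≤0.3% |
| 5 / 25, Day 15 predose raised 20–25 | own-day predose | 2.5–5 | about 100% | ≤0.3% |

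The first two rows sit exactly on the limit, where the nominal rate is at most 5%.

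**5. Power cost.** At a true 5 ms on both days, eight pooled contrasts all pass in 96–100% of trials. Sixteen contrasts give 79% with a single-reading baseline. With the mean of two predose readings they give 86–91%, the lower figure when the SE assumes equal variance. The independence formula gives 0.9707¹⁶ = 62%, which is too low because the contrasts share a baseline.

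**6. Plasma against whole blood.**

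- At the threefold ratio, a zero-intercept model with a true 20 ms at blood Cmax predicts 20/3 = 6.7 ms. With an intercept of 5 ms and a slope part of 15 ms it predicts 5 + 15/3 = 10 ms instead of 20.
- As a second route, take Bmax 309 and kd 23.5 µg/l (Protocol Table 2), the median Cmax of 82.6 ng/ml at 5 mg/m² (Protocol Section 1.3.4.3.1, read as blood), and an assumed hematocrit H of 0.26–0.40. Solve (1 − H)Cp + H × 309Cp/(23.5 + Cp) = 82.6. Then Cp = 42.0 (H = 0.26) or 27.2 (H = 0.40), so the plasma-to-blood ratio is 0.51 or 0.33.

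**The case against.** The best opposing case is that the primary rule pools two identical infusions on purpose. Change over the treatment period is a separate secondary objective (Section 2), and the shift would be visible: in the absorbed case the day term has SE 18√(2/(36 × 8)) = 1.5 ms, so a 20 ms shift stands out at about 13 standard errors. Section 8.3 also examines period effects on slope and intercept. That is true of a uniform shift, but not of a rise at one Day 15 time point. None of these outputs, nor the outlier tables (which are by time point, not day), carries a rule that would block the non-inferiority conclusion. The synopsis and Section 7.3.2 define the change by day, so the day-specific target is the protocol's own.

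It is fair that the size depends on coding: with baseline in both days, the uniform 5/25 case passes in only 7–19%. The raised-predose case is also the least likely, since Section 1.2 calls Day 15 residual concentrations negligible and Protocol Section 1.3.4.3 reports minimal accumulation and no time-dependent kinetics. If the effect is equal on both days, the model works. But the single-time-point rise passes about half the time under every coding.

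The separate QTc analysis document (SAP Section 8.12) was not available and may add day-specific contrasts. Appendix 8 nevertheless states the model and the rule as they stand.

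A Day 1 baseline in an uncontrolled substudy does attribute two weeks of drift to plitidepsin. That cost already follows from Section 7.3.2.

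On the second issue, plasma may be a wording slip, and the complementary whole-blood analysis in Section 8.3 partly offsets it. The plasma values of 27.2–42.0 also exceed kd, although Protocol Section 1.3.4.3 says phase II plasma levels lie below it. Lower plasma values make the understatement larger: at Cp = 23.5 the ratio is 23.5/(0.74 × 23.5 + 0.26 × 154.5) = 0.41 for H = 0.26, and 0.31 for H = 0.40.

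**Conclusion.** The concern holds and should be fixed. As written, the 20 ms rule does not test Day 15, and its error rate against a Day 15 mean exactly on the limit is 43–99% (all times) or 72–84% (end of infusion only), where at most 5% is intended. The spread reflects the unresolved baseline coding; no coding brings the rate near 5%. These figures assume 36 evaluable patients, independent residuals with SD 18 ms and the additive model as listed. They do not suggest that a Day 15 rise is likely, only that the rule would often miss one.

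The plasma–blood mismatch is plain in the text. Taken literally, it leaves about one third of the slope part of the prediction (0.33–0.51 by the binding model), less severely in total if an intercept is retained.

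Both points bear on a safety conclusion in the substudy and do not affect the PFS analysis.

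**What to change.** - In Section 8.2, add the time-by-day interaction or analyse each day separately, and require the upper limit to be below 20 ms for all 16 time-by-day contrasts.
- Measure both days against the Day 1 baseline of Section 7.3.2, including its Predose 2 switch rule. State how baseline enters the model, and bring Sections 1.2 and 7.5 into line.
- In Section 8.3, evaluate the predicted change at the mean whole-blood Cmax.
- Carry the same wording into the separate QTc analysis document.

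This takes a few sentences and no new data. The cost is joint power at a true 5 ms: from 96–100% under the pooled rule to 79% with a single-reading baseline, close to the stated 80%, or 86–91% with the mean of two predose readings.
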